5.3 BROXY M REGULATORY STATUS AND INTENDED USE

BrOxy M is a CE marked, Class IIa medical device.

According to the User Manual, the BrOxy M intended use is as follows:

- The device is dedicated to recording signals for photoplethysmographic use in the red and infrared frequency, through a wearable module placed on the subject's wrist;
- The device allows the recording and storage of the signals described above, their transfer to the memory of a personal computer and their storage through a software module;
- The software allows to export the recorded signals for further analysis and measurements performed by means of specific algorithms and/or processes possibly developed by the user himself, under his/her responsibility;
- The signals recorded with the device can be used for diagnostic purposes (for example, heart rate calculation, SpO₂ measurement, etc.) as long as they are suitably processed, under the direct responsibility of the user, with appropriate software for medical use provided by Life Meter S.r.l. and/or other compatible software.

The typical contact duration between BrOxy M and the subject's wrist is 24 hours. BrOxy M can be used by subjects of all ages having wrist diameter between 150 and 200 mm and provided that the skin of the

Clinical Investigational Plan			
Protocol No.:	Version 1.0	Page 20 of 45	
01M2020-CH.LMD	Date: 22 December 2020	rage 20 01 43	

wrist where the device will be placed is intact and healthy. No other contraindication exists for the use of BrOxy M.

In this study, BrOxy M will be used on healthy volunteers accepting to participate in a controlled desaturation study, in full accordance with the limitations imposed by and instructions included in the BrOxy M User Manual. The purpose of this study is to confirm the performance of BrOxy M in comparison with a reference, CE marked, pulse oximeter equipment. The study will follow the procedures described in the standard ISO 80601-2-61:2017 "Medical electrical equipment - Part 2-61: particular requirements for basic safety and essential performance of pulse oximeter equipment".

6 REFERENCE MEDICAL DEVICE

The device used as the reference for measuring SpO₂ and heart rate is the Nellcor™ Bedside Respiratory Patient Monitoring System model PM1000N (Covidien LLC, USA). It is a CE marked device normally used in a hospital environment for monitoring patients while they are in bed. The Nellcor pulseoxymeter will require the use of the Nellcor™ Adult XL SpO₂ Sensor mod. MAXALI (sterile, single-use only).

In addition to being a precise device for measuring HR and SpO₂, it allows the storage of the displayed measurements and the downloading of data on a PC memory via USB. These features make the Nellcor™ mod. PM1000N suitable to be employed as reference device in this clinical trial.

The main features of the Nellcor mod. PM1000N are as follows:

- Precision on adult subjects, even with low perfusion:
 - Error +/- 2 digits, on the 70-100% range of SpO₂;
 - Error +/- 3 bpm, on the 20-250 bpm range of HR;
 - The measurements used as a reference were carried out on healthy, voluntary subjects, by means of the use of a CO-oximeter with analysis of arterial blood samples.
- Data and measurement recording:
 - Up to 48 hours of recording
 - Sampling: 1 measure per second
 - USB connection to download recorded data (SpO₂ and heart rate recorded values) by means of specific software;
 - Downloaded data shows time indication (hour, minute and second) and operating status, indicating signal quality such as motion, alarms, loss of pulse, etc.
- Alarms:
 - Acoustic and visual feedback to report critical conditions;
 - Possibility to customize the alarm levels (for threshold value and minimum duration of the event);
- Product compliance:
 - o IEC 60601-1:2005

Clinical Investigational Plan			
Protocol No.:	Version 1.0	Page 21 of 45	
01M2020-CH.LMD	Date: 22 December 2020	1 agc 21 01 43	

o IEC 60601-1-2: 2007

o IEC 80601-2-61:2001

The rationale for the selection of the reference device is that it meets the requirements specified in the standard ISO 80601-2-61:2017, section EE.3. In particular, the Nellcor™ Bedside Respiratory Patient Monitoring System model PM1000N has been calibrated against:

1) a Co-Oximeter for measuring \mbox{SpO}_2 and

2) an ECG for measuring cardiac frequency.

7 OBJECTIVES AND ENDPOINTS

7.1 OBJECTIVES

The **primary objective** of the study is to confirm the performance of BrOxy M in comparison with a reference, CE marked, pulse oximeter equipment in a controlled desaturation study.

The **secondary objectives** of the study are:

- To assess BrOxy M performance in subjects with different skin pigmentation (Note: this is a tentative objective, since few subjects are planned to be enrolled and there is no guarantee that they will have different skin pigmentation)
- to confirm BrOxy M safety

7.2 ENDPOINTS

The **primary endpoint** of the study will be a comparison of the accuracy of SpO_2 and HR measurements obtained with BrOxy M with that obtained with the reference pulse oximeter in paired observations over a range between 80% and 100% SpO_2 .

For each subject, four different saturation plateaus will be set up (i.e. at 97%, 92%, 87% and 82% SpO_2), waiting 30" before starting to keep the SpO_2 level on each plateau for 2.5' in order to obtain 8 measurements in post-processing. These measurements will be at least 20" away from each other, for a total of 32 measurements for each subject, as summarized in Table 1.

The study will follow the procedures described in the standard ISO 80601-2-61:2017 "Medical electrical equipment - Part 2-61: particular requirements for basic safety and essential performance of pulse oximeter equipment".

As **secondary endpoints**, the following will be verified:

• whether any relation exists between the accuracy of BrOxy M for both SpO₂ and HR and subject skin pigmentations as measured with the Fitzpatrick scale.

Clinical Investigational Plan			
Protocol No.:	Version 1.0	Page 22 of 45	
01M2020-CH.LMD	Date: 22 December 2020	1.80 == 0. 10	

• that no adverse events related to the use of BrOxy M, besides a temporary slight skin irritation of the wrist, will occur.

8 RISK BENEFIT ASSESSMENT

8.1 BENEFITS

Enrolled subjects will not receive any direct benefit from participating in the study besides the possibility to have some clinical parameters assessed at screening, e.g. ECG, hemoglobin, etc.

8.2 RISKS

Each subject enrolled in the study will be exposed to experimentally generated, controlled hypoxia, starting from $97\% O_2$ and reaching $83\% O_2$ as the lowest level. During the desaturation protocol, which is expected to last a maximum of 35 minutes for each subject, SpO_2 and cardiac frequency will be measured continuously using BrOxy M and the reference device.

The following considerations were made about the potential risks that subjects enrolled in this study will be exposed to:

- Risks associated to the use of BrOxy M and the reference device are negligible, i.e. for BrOxy M a slight irritation of the skin where the bracelet is placed can sometimes be expected. For the reference device subjects may exhibit allergic reactions to the adhesive tape. For this reason subjects with known allergy to adhesive tapes should be excluded from the study
- The absence of pre-existing cardiovascular or pulmonary disease that may expose subjects to increased risks when participating in the study will be carefully checked at screening (see exclusion criteria in Section 10.2)

It is expected that, due to the use of a controlled desaturation protocol foreseen by the standard ISO 80601-2-61:2017, this study is classified as an interventional post-market clinical study in accordance with Annex I of EN ISO 14155:2020.

- Values may be below 90% for a maximum continuous period of 3 minutes. The Principal Investigator will be equipped with a chronograph with a timer and alarm function to avoid exposure of the subjects to longer periods of hypoxia.
- The lowest SpO₂ that subjects will be exposed to is 82% for maximum 3 minutes (30" for stabilization and 2.5' for signal recording). This situation is similar to the one that a subject would have by staying at an altitude of around 3,500-4,000 meters for 3 minutes. Data in literature indicate that there are no risks for healthy subjects for permanence time below 30 minutes at altitudes up to 5,500 m (32).
- The full test will be performed only once on each subject.
- The study will be performed in an outpatient pneumology department, where medical assistance can be promptly provided if necessary.

Clinical Investigational Plan			
Protocol No.:	Version 1.0	Page 23 of 45	
01M2020-CH.LMD	Date: 22 December 2020	.0-	

• The experience of research laboratories performing desaturation studies involving up to 10,000 subjects exposed to arterial saturation levels as low as 45% for brief periods, indicates that brief hypoxia levels much higher than those in this study (i.e. SaO₂ 50%-70% for 10-30 minutes) is well tolerated in healthy individuals with normal cardiopulmonary function (33).

In light of the above considerations the Sponsor believes that all potential risks related to study participation have been minimized. As a result, residual risks are minimal and can be considered acceptable.

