The study protocol follows the requirements of the standard ISO 80601-2-61:2017 "Medical electrical equipment - Part 2-61: particular requirements for basic safety and essential performance of pulse oximeter equipment". As such, in this study BrOxy M and the reference device will be tested on healthy volunteers accepting to participate in a controlled desaturation study. Use of both devices will be in accordance with the limitations imposed by and instructions included in the BrOxy M and Reference device User Manual.

Due to the use of a controlled desaturation protocol foreseen by the standard ISO 80601-2-61:2017, this study is classified as an interventional post-market clinical study in accordance with Annex I of EN ISO 14155:2020.

Clinical Investigational Plan		
Protocol No.:	Version 1.0	Page 15 of 45
01M2020-CH.LMD	Date: 22 December 2020	

During the execution of the protocol, the following measurements will be acquired in continuous mode:

- 1) the SpO₂ and HR values from the reference device, and
- 2) the photoplethysmographic signals with BrOxy M.

As shown in Figure 1, the protocol provides for the maintenance of 4 plateaus at 4 different values of saturation in steps of 5% and, therefore, at 97%, 92%, 87% and 82% SpO_2 . The SpO_2 value displayed on the reference device will be used to check the saturation level reached during each plateau level. For each level, at least 30" will be expected in order to stabilize the SpO_2 value and, subsequently, the plateau will be maintained for 2.5', continuing the parallel acquisition with both the reference device and BrOxy M.

[figure not shown]

Figure 1: Time distribution of the SpO₂ measurements to be carried out on each individual subject.

Four different saturation plateaus will be used, waiting for the plateau stabilization before starting the 2.5' signal recording from which the series of 8 measurements with at least 20' of pause are extracted by means of a post-processing algorithm.

After data acquisition, up to 8 measurements for SpO₂ and HR will be selected from each plateau as follows:

- Reference device: SpO₂ and HR values will be selected starting from at least 30" after plateau stabilization, with a time interval between measurements of at least 20".
- BrOxy M: SpO₂ and HR values generated by BrOxy M will be obtained by processing the
 photoplethysmographic signals generated by the device with the BrOxy Medical software. Then,

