 SpO₂ and HR values corresponding to the same time points selected for the reference device will
 be chosen.

Clinical Investigational Plan		
Protocol No.:	Version 1.0	Page 16 of 45
01M2020-CH.LMD	Date: 22 December 2020	1 486 10 01 13

As a result, it is expected that from each enrolled subject up to 32 paired measurements of SpO_2 and HR will be obtained from the reference device and BrOxy M. Table 1 below summarises the data collection process.

Plateau no.	Range SpO₂ (%)	Inhaled solution	Plateau duration	No. of Measurements of SpO ₂ and HR extracted from recordings
1)	95 – 100 (target 97%)	Ambient air (medical air)	2.5'	8
II)	90 – 94 (target 92%)	O2 15% + N 85%	2.5'	8
III)	85 – 89 (target 87%)	O2 13% + N 87%	2.5'	8
IV)	80 – 84 (target 82%)	O2 11% +N 89%	2.5'	8
			Total	32 measurements

Table 1: Number of measurements to be performed for each subject, for each target level of SpO₂ and indication of the gaseous solution inhaled during each target level.

After completing the study on 10 subjects, collecting around 320 paired measurements it will be verified that, by dividing the desaturation interval into three equal parts, each part contains around a third of the measurements made. Therefore, considering the minimum target number of 200 measurements (per EN 80601-2-61 standard) and the interval between 98% and 82% of SaO_2 to be divided into three parts, at the end of the protocol on all the subjects recruited, it is expected to have:

- At least 67 measurements between 98% and 93% of SpO₂;
- At least 67 measurements between 92% and 87% of SpO₂;
- At least 67 measurements between 86% and 82% of SpO₂

In the event that this minimum target is not reached to meet the requirements of the EN 80601-2-61 standard, it may be necessary to recruit up to 2 additional subjects.

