At this point, once all the above conditions are verified, the values of SpO_2 and HR are calculated for the signal windows considered. These values are considered acceptable if the following conditions occur at the same time:

- Heart rate values between 40 and 280 bpm
- SpO₂ values between 80 and 100 %

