17.3 DATA PROCESSING

Subject's data from the paper CRF will be entered manually on an electronic clinical database.

Measurements obtained with the reference device and with BrOxy M will be accessed by the Sponsor Data Manager, and processed as follows. After data acquisition from the devices, first 8 valid paired assessments of SpO_2 and HR will be selected from each plateau as follows:

- Reference device: SpO₂ and HR valid values will be selected starting from at least 30" after plateau stabilization, with a time interval between measurements of at least 20".
- BrOxy M: SpO₂ and HR values generated by BrOxy M will be obtained by processing the
 photoplethysmographic signals generated by the device with the BrOxy Medical software. Then,
 SpO₂ and HR values corresponding to the same time points selected for the reference pulse
 oximeter will be chosen.

As a result, it is expected that up to 32 paired (and synchronized) measurements of SpO₂ and HR will be obtained from each enrolled subject, from the reference device and BrOxy M. Once paired measurements for SpO₂ and cardiac frequency have been obtained at the preselected time points (0, 20", 40", etc.) the list of paired observations will be merged with subject's data in the clinical database.

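### Section 8.2 states a hypoxia floor that Table 1 goes below, and a 3-minute limit below 90% SpO2 that plateaus III and IV each use up with no slack

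*Combined protocol and SAP*

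**What the plan says.** **Floor.** Section 8.2 opens by naming 83% as the lowest level. A later bullet says the lowest SpO2 "that subjects will be exposed to is 82% for maximum 3 minutes", and breaks the 3 minutes down as 30 s of stabilisation and 2.5 minutes of recording. Table 1 (Section 3, repeated in Section 11.2 and in the synopsis) gives the plateau IV range as "80 – 84 (target 82"%). Section 7.2 sets the primary endpoint over 80-100% SpO2.

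**Time.** Section 8.2 states: "Values may be below 90% for a maximum continuous period of 3 minutes". It gives the Principal Investigator a chronograph with an alarm so that longer hypoxia is avoided. In Table 1, both plateau III (85-89%) and plateau IV lie wholly below 90%. Section 3 makes the 30 s stabilisation a minimum and then holds the plateau for 2.5 minutes. Sections 7.2 and 11.2 ask for 8 readings per plateau, at least 20 s apart. Section 3 is softer: "After data acquisition, up to 8 measurements for" SpO2 and HR are selected from each plateau. Section 8.2 puts the whole desaturation protocol at no more than 35 minutes.

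**The concern.** Section 8.2 is where the plan states how much hypoxia healthy volunteers will undergo, and Section 8 then concludes that the remaining risk is minimal. Those volunteers gain nothing directly beyond some screening results (Section 8.1). The stated exposure should therefore be one that the test schedule can keep to.

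The floor is not: following Table 1 can take a subject below it. The time limit leaves nothing for ordinary variation. When the timer sounds before a plateau is complete, the text does not say whether the 3-minute limit or the full plateau with 8 readings comes first.

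**Working it through.** **Floor, statements side by side**

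| Place | Lowest SpO2 |
|---|---|
| Section 8.2, first statement | 83% |
| Section 8.2, later bullet | 82% |
| Table 1, plateau IV | 80% (target 82%) |
| Section 7.2, endpoint range | 80% |

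Plateau IV permits five whole-number levels: 80, 81, 82, 83 and 84. Two lie below 82% and three lie below 83%. The largest gap is 82 - 80 = 2 points or 83 - 80 = 3 points. Section 17.2 also accepts "values between 80 and 100"%, but that is a filter on calculated readings and does not set exposure. Table 1 carries the point.

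**Time, the plan's own figure.** 30 s + 150 s = 180 s = 3 minutes. This reproduces Section 8.2.

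**Time, slack.** Let S be the stabilisation time, x the part of it spent above 90%, and R the time to climb back to 90% after the plateau. The continuous run below 90% is

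run = S - x + 150 + R.

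- S = 30, x = 0, R = 0: run = 180 s, so the margin is 0 s.
- S = 30: run = 180 - x + R, so the limit holds only if R is no larger than x, and x cannot exceed 30 s.
- x = 0, R = 0, with S = 45, 60 or 90 s (assumed values): run = 195, 210 or 240 s, that is 3.25, 3.5 or 4.0 minutes.

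The documents give neither x nor R.

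**Between plateaus III and IV.** Four plateaus take 4 x 3 = 12 minutes. Against the 35-minute maximum, 35 - 12 = 23 minutes are unallocated, or about 23/3 = 7.7 minutes per gap if shared over the three gaps.

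**Readings if the limit takes priority.** Take the first reading at 30 s, with the clock starting at the same moment as the stabilisation wait. Eight readings span 7 x 20 = 140 s, so the eighth falls at 170 s and leaves 10 s to regain 90%. In general,

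n = min(8, floor((180 - 30 - R)/20) + 1).

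| Assumed R | n per plateau (III, IV) | Pooled, 10 subjects: 10 x (16 + 2n) | Plateau IV, 10 subjects | Plateau IV, 12 subjects |
|---|---|---|---|---|
| 10 s | 8 | 320 | 80 | 96 |
| 30 s | 7 | 300 | 70 | 84 |
| 60 s | 5 | 260 | 50 | 60 |

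All pooled counts exceed the minimum of 200. For the lowest third, Section 3 wants "At least 67 measurements between 86% and 82"%. Plateau III readings at 85-86% count there as well, while readings at 80-81% do not. The counts are before losses to signal quality.

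**The case against.** The strongest reply is that Section 8.2 derives its 3 minutes from the schedule, so the nominal plan meets its own limit. An overrun needs facts the text does not give: when the clock starts, how much of the 30 s is above 90%, and how fast subjects recover. That stands, and the time point is therefore one of no slack.

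Two stronger readings are tempting, and neither is supported.

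- A reader might infer that plateaus III and IV run back to back, giving at least 6 minutes below 90%, twice the limit. The text names successive gases and no return to air. But the time course is in Figure 1, which is not shown, and 23 unallocated minutes leave room for recovery.
- A reader might add the 30 s in Section 17.3 to the stabilisation wait and place the eighth reading at 30 + 30 + 140 = 200 s. Sections 7.2, 8.2 and 11.2 describe a single 30 s wait. On the longer count the plateau would simply yield fewer readings.

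Controls also exist: the chronograph, the alarm check in Section 11.2, the pre-study tests of gas delivery times in Section 13, and deviation review in Section 19. Section 10.5 says how an interrupted session is recorded and that its valid measurements are kept. Section 11.2 promises separate written instructions, which may hold alarm settings. These limit the consequence. They do not reconcile 83%, 82% and 80%, and Section 10.5 does not say when the timer should end a plateau.

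Finally, the reference device has a stated error of 2 digits either way (Section 6), so a displayed 80-81% is within error of 82%. That is a reason to state a floor the display can respect.

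**Conclusion.** The floor conflict is established from the text alone: Section 8.2 disagrees with itself by 1 point and with Table 1 by 2 to 3 points. On time, each of plateaus III and IV takes at least 180 s against a limit of 180 s. That figure assumes none of the 30 s is above 90% and ignores the climb back. The documents do not show that the limit will be broken.

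This is a minor correction of stated safety limits. Subjects are ASA 1, aged 18-50 and tested in an outpatient pneumology department, and Section 8.2 cites good tolerance of deeper and longer hypoxia. The sample size and the analysis do not depend on it.

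**What to change.** (a) In Section 8.2, replace 83% and 82% with one floor that matches Table 1: exposure may reach 80%, with a target of 82%. In Section 11.2, set the reference alarm so that a value below 80% returns the subject to medical air.

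Narrowing plateau IV to 82-84% with a target of 83% is less attractive. It drops valid 80-81% readings inside the endpoint range, and leaves 1 digit of margin against a reference error of 2.

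(b) In Sections 8.2 and 11.2, state that:

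- the 3-minute clock runs from first crossing 90% until SpO2 is back at 90%;
- subjects return to at least 90% between plateaus III and IV;
- the limit takes priority over the full 2.5 minutes and the 8 readings, which Section 3 already allows by asking for up to 8.

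If the set-up subject shows that this cannot be met, restate the limit to the true run.

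**Cost.** A few lines of text and Ethics Committee approval of the amended wording (Section 18). Some readings on plateaus III and IV may be lost: 0, 1 or 3 per plateau for an assumed recovery of 10, 30 or 60 s. If recovery is slow enough to threaten the count in the lowest third, restating the limit avoids the loss.

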11.2 VISIT 1 – TEST SESSION (DAY 1)

The study involves, starting from medical air (O2 concentration 20.98%), the subsequent use of cylinders with an oxygen concentration of 15%, 13% and 11%, rest nitrogen. We will use a Hans Rudolph one-way valve connected to the subject with a nose piece to eliminate nasal ventilation and with a disposable mouthpiece and filter. The valve on the inhalation side will be connected, with a two-way tap, to a Douglas bag supplied by the gas cylinder with a concentration selected according to the target level of SpO_2 to be obtained (see Table 1).

From each session of measurements on each subject, the photoplethysmographic signals in the red and infrared frequency will be collected from the subject's wrist, while the comparison measurements will be carried out using the reference oximeter.

As shown in Figure 1, during the execution of the protocol, four different saturation plateaus will be used (in steps of 5% and, therefore, at 97%, 92%, 87% and 82%), waiting 30" before starting to keep the SpO₂ level on each plateau for 2.5' in order to obtain 8 measurements in post-processing. These measurements will be at least 20" away from each other, for a total of 32 measurements for each subject as summarized in Table 1 (on page 17 and replicated below).

Plateau no.	Range SpO₂ (%)	Inhaled solution	Plateau duration	N. of Measurements of SpO ₂ and HR extracted from recordings
1)	95 – 100 (target 97%)	Ambient air (medical air)	2.5'	8
II)	90 – 94 (target 92%)	O2 15% + N 85%	2.5'	8
III)	85 – 89 (target 87%)	O2 13% + N 87%	2.5'	8
IV)	80 – 84 (target 82%)	O2 11% +N 89%	2.5'	8
			Total	32 measurements

Clinical Investigational Plan			
Protocol No.:	Version 1.0	Page 28 of 45	
01M2020-CH.LMD	Date: 22 December 2020	rage 28 01 43	

Table 1: Number of measurements to be performed for each subject, for each target level of SpO₂ and indication of the gaseous solution inhaled during each target level.

[figure not shown]

Figure 1: Time distribution of the SpO_2 measurements to be carried out on each individual subject. Four different saturation plateaus will be used, waiting the plateau stabilization before starting the 2.5' signal recording from which the series of 8 measurements with at least 20' of pause are extracted by means of a post-processing algorithm.

Before starting the measurement protocol, as shown in Figure 1, in order to prepare the above instrumentation, it is necessary to carry out the following operations:

- 1. Start the PC;

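### The 3-minute limit on continuous time below 90% SpO2 is not reconciled with two plateaus that lie wholly below 90%: it is exceeded if they run in succession and has no slack if they are separated

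*Combined protocol and SAP*

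**What the plan says.** Section 8.2 of the combined protocol and SAP states the exposure limit: "Values may be below 90% for a maximum continuous period of 3 minutes". It adds that the principal investigator will have a chronograph with timer and alarm so that longer hypoxia is avoided. The same section gives the lowest level, 82%, a maximum of 3 minutes, made up of 30 s for stabilisation and 2.5 minutes for recording. It caps the whole desaturation protocol at 35 minutes.

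Section 3 describes the schedule: "the protocol provides for the maintenance of 4 plateaus at 4 different values of saturation in steps of 5" per cent. In Table 1, plateau III covers 85–89% (target 87%) and plateau IV covers 80–84% (target 82%). Section 3 allows at least 30 s for each level to stabilise, and then "the plateau will be maintained for 2.5" minutes. Sections 7.2 and 11.2 give the wait as a plain 30 s.

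Section 11.2 gives the order of gases: "starting from medical air (O2 concentration 20.98%), the subsequent use of cylinders with an oxygen concentration of 15%, 13% and 11" per cent. The time course is drawn in Figure 1, which is not visible to this review. No visible sentence says what is inhaled between plateaus III and IV, or when the timer is started or reset.

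**The concern.** Section 8.2's own count for a single plateau (30 s plus 2.5 minutes) already equals the full 3-minute allowance, and the schedule contains two plateaus below 90%. If IV follows III directly, the limit cannot be kept. If the two are separated, it can be kept only if no further time is spent below 90% on the way down or back.

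The limit matters because it is part of the basis on which the protocol calls the residual risks minimal and acceptable. It is also meant to be enforced with an alarm, so site staff need to know what it applies to. A site that reads the prose as a direct descent would exceed the stated limit in every subject who completes the session. A site that reads it as separated episodes has no written instruction for the interval.

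**Working it through.** **Inputs**

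- Limit on continuous time below 90%: 3 min (Section 8.2).
- Stabilisation per level: at least 0.5 min (Section 3); counted as 0.5 min in Section 8.2.
- Hold per level: 2.5 min (Section 3, Table 1).
- Plateau ranges: III 85–89%, IV 80–84% (Table 1).
- Maximum length of the desaturation protocol: 35 min (Section 8.2).

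**Step 1. The plan's own figure.** One plateau = 0.5 + 2.5 = 3.0 min. This reproduces the 3 minutes that Section 8.2 gives for the lowest level.

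**Step 2. Plateaus III and IV in succession.** The answer depends on how plateau III's stabilisation is counted.

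| Count | Sum | Minutes below 90% | Ratio to 3 min |
|---|---|---|---|
| Both stabilisations below 90% | 2 × (0.5 + 2.5) | 6.0 | 2.0 |
| All of III's stabilisation at or above 90% | 2.5 + 0.5 + 2.5 | 5.5 | 1.8 |
| The two recordings only | 2 × 2.5 | 5.0 | 1.7 |

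Every count exceeds 3 minutes. The last row is a lower bound, because it leaves out the step from III to IV, which would itself be spent below 90%.

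**Step 3. Plateaus III and IV separated by a return to 90% or above.** Let d be any time below 90% while falling to the plateau that is not already inside the 0.5 min, and u the time below 90% while returning.

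Continuous time below 90% = d + 3.0 + u.

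This is within 3 minutes only if d = u = 0 and stabilisation takes exactly 30 s. Plateau IV is the binding case, because Section 8.2 counts its full 3 minutes at the lowest level; passing between 82% and 90% then comes on top. For plateau III, up to 0.5 min could be gained if its stabilisation took place at or above 90%, but that does not help plateau IV. Since Section 3 makes 30 s a minimum, any longer stabilisation below 90% adds to the total.

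**Step 4. Is there room for a separation?** Four plateaus = 4 × 3.0 = 12 min. Unallocated time = 35 − 12 = 23 min, or 23 / 3 ≈ 7.7 min for each of three gaps. The time budget therefore does not exclude intervals between plateaus, but no visible sentence assigns the 23 minutes to them.

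**The case against.** The strongest reply is that direct succession is nowhere stated. Steps of 5% describe the spacing of the targets, not their timing, and an order of cylinders does not exclude air between them. The sequence may be drawn in Figure 1, and what a missing figure would show cannot be called absent from the plan. The visible text also fits separate episodes: the limit is worded as continuous, it equals exactly one plateau, and 23 of the 35 minutes are otherwise unexplained. Section 11.2 further promises detailed written instructions and training. All of this stands, and it limits the point to a conditional one.

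It does not remove the point. Even if the figure shows a recovery, the visible prose does not tell the site to carry one out or say when the timer resets. The lack of slack in Step 3 applies whether or not the plateaus are separated.

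A reader might infer three stronger conclusions that the documents do not support:

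- **A proven contradiction.** This would require direct succession, which the visible text suggests but does not state.
- **At least 6 minutes, or at least twice the limit.** Six minutes is the top of the range. Part or all of plateau III's stabilisation may be at or above 90%, which gives 5.5 minutes.
- **Loss of a quarter of the data.** Plateau IV supplies 10 × 8 = 80 of 320 planned pairs (25%), but they would be lost only if the alarm ended the session. Section 8.2 does not say that it does, and Section 10.4 does not list it as a reason for ending participation early.

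**Conclusion.** The point holds as an unresolved inconsistency about a stated subject-safety limit. If plateaus III and IV run in succession, continuous time below 90% is about 5.5 to 6 minutes, and no less than 5.0 minutes, against a maximum of 3. If they are separated, each takes 3.0 minutes on Section 8.2's own count plus any time below 90% going down and coming back, so the limit leaves no margin.

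The first result assumes no return to 90% or above between III and IV. The second assumes the protocol's count of 30 s plus 2.5 minutes. Neither rests on a figure from outside the document. Figure 1 may settle which case applies, but it would not by itself create slack in the second. No error in the statistical analysis follows from this; the issue is whether the schedule and the limit can both be met as written.

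**What to change.** Reconcile Section 8.2 with Sections 3 and 11.2, Table 1 and Figure 1 before the first subject is tested:

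- State in Section 11.2 the sequence between plateaus III and IV, including what is inhaled and whether SpO2 is at or above 90% before plateau IV begins.
- State when the 3-minute timer starts, when it resets, and what the site does when it alarms.
- Settle whether 30 s of stabilisation is a minimum (Section 3) or part of a fixed maximum (Section 8.2).
- Make the stated maximum and the schedule mutually achievable, counting time below 90% during the fall and the return.

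Which of the two governs, and what the values should be, is for the clinical staff and the sponsor to decide.

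The cost is protocol wording, a timing row in Table 1 and a check of Figure 1 and the written site instructions, with Ethics Committee review as Section 18 requires for an amendment. The clarification itself needs no extra subjects.
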